**Long-term Quitting Study**

We have engineered a recruitment strategy that models attrition and subject loss, resulting in good power under conservative assumptions. In this project, ~1000 smokers will receive a Usual Care cessation treatment. Based on other trials, we anticipate that 72% of the  $N \approx 1000$  smokers will relapse in the first 6 months (i.e.,  $n \approx 720$ ; see Figure 3); we believe that 20% will remain abstinent and 8% will attrit. Of the 720 relapsers, we predict that 85% will enter RR Preparation treatment ( $n = 612$ ) at some point in the 6 months after their quit day, while 15% ( $n = 108$ ) will stop participating. The 612 participants who continue in treatment will be randomized to the 3 RR Preparation intervention conditions: the Low-Contact control condition ( $n \approx 150$ ), the Recycling condition ( $n \approx 225$ ) and the Reduction condition ( $n \approx 225$ ). Of 450 assigned to the Recycling and Reduction conditions, we believe that 10% ( $n \approx 45$ ) will never make a new quit attempt, another 30% ( $n \approx 135$ ) will quit on their own or attrit without entering RR Cessation treatment, leaving 60% ( $n \approx 270$ ) who will enter RR Cessation treatment, and be randomized to the 2 RR Cessation intervention factors ( $n \approx 135$ /each level of each factor).

**Figure 3.** Participant Flow with Estimated Ns

We have computed power for Primary Aim 1: to determine the effect of the RR Preparation factors on abstinence assessed at 14 months after randomization to RR

“Breaking Addiction to Tobacco for Health (BREATHE) Study”

PI: [name], MPH, MBA; UW-CTRI Center Grant: 1P01CA180945-01.

Preparation treatment. We computed power for the GLMM longitudinal analysis using the SAS macro developed by Dang and colleagues. We used the following parameters: N=600 in the intent-to-treat comparisons involving all 3 RR Preparation conditions (Control n = 150, and n's = 225 for each active condition), and N = 450 for comparisons of the two active Preparatory conditions. Smoking status will be analyzed at 1 time point (Month 14 after randomization to RR Preparation treatment); a 10% attrition rate across follow-up; with the treatment effect modeled as consistent over time; random effects variance=1; and within-subject correlation=0.6. We hypothesize average abstinence rates to be 15% for the Control condition, 25% for the Recycling condition, and 35% for the Reduction condition. We propose that any increase in abstinence of 15% or higher would be clinically significant. For the purpose of the power analysis we will assume a 15% abstinence rate for the Control condition. Under this scenario, there would be insufficient power to detect an effect for the Recycling condition versus the Control condition (i.e., 15% vs. 25%), but power would exceed .80 if the Reduction treatment produced an abstinence rate of .28 or higher. If we assume a 10% abstinence rate for the Control condition, power would exceed .80 if either the Recycling condition or the Reduction condition produced an abstinence rate of .21 or higher. We did not power the study to demonstrate a significant difference between the two active conditions. Therefore, we anticipate that only the RR Reduction treatment will significantly increase long-term abstinence rates over those produced by the Usual Care control condition.

We also computed power for the Secondary Aim of determining the effect of the RR Preparation factor on the likelihood of a meaningful quit attempt characterized by more than one day of abstinence (that occurs at some point in the 12 months following entry into RR Preparation treatment). For power analyses we will restrict this comparison to the two active RR Preparation treatments since they yield the more conservative test. We predict that 60% of the 225 participants receiving Recycling Counseling will make a meaningful quit attempt, while 80% of the 225 participants receiving Reduction Counseling will make a meaningful quit attempt over the 12 months following entry into the RR Preparation treatment. Thus we predict a 20 percentage point difference (with 60% vs. 80% of participants making a meaningful quit attempt); we have power of > .85 to detect this effect. With a 15 percentage point difference (e.g., 60% vs. 75% or 65% vs. 80%) power remains > .80. The estimate of a 60-65% base rate of meaningful quit attempts is taken from the rate of quit attempts among smokers in general: i.e., with no preparation treatment ~40-45% of smokers a year make a quit attempt. We believe that Recycling Counseling will increase this figure by about 40-50% based upon the impact of Recycling Counseling on acceptance of pharmacotherapy when it is offered. Therefore, we assume that 60% of the Recycling participants will make a meaningful quit attempt, and we further propose that a 15-20 percentage point increase in meaningful quit attempts is a clinically worthwhile effect, given the strong relation between early quitting success and later abstinence.

We have not powered this study to detect significant effects for the other data comparisons offered as Secondary Aims (e.g., transitions across phases of chronic care treatment, the effects of RR Cessation treatments). Rather, those Aims are included in this research so that we can gather additional evidence related to the feasibility of a chronic care approach to smoking and so that we can gather additional preliminary data to guide our future research and treatment development.

**Clinic Randomized Control Trial**

“Breaking Addiction to Tobacco for Health (BREATHE) Study”

PI: [name], MPH, MBA; UW-CTRI Center Grant: 1P01CA180945-01.

The primary outcome will be treatment engagement and we will analyze this with repeated measures analysis of variance (ANOVA) and analysis of covariance (ANCOVA). In these analyses we will contrast the experimental and control (F2Q) clinics on the basis of treatment engagement means averaged over the periods of clinic participation (which may differ somewhat across clinics) pre and post implementation. Since data on the dependent variables will be routinely collected pre-implementation, we have opportunity to determine the length of the baseline period: we will average data over 6 months to establish a baseline. The analyses will, conservatively, use the clinic as the unit of analysis. ANCOVA will use clinic location (rural vs. urban), size, SES, and baseline rates of smoker documentation and referral as covariates. We will conservatively use ANOVA to estimate power, in part, because it is unclear how much this set of covariates will affect error within the ANCOVA. Based on earlier data, we anticipate treatment engagement will be 1% for both groups at baseline (for the 6 months pre-implementation) and 10 and 2% post-implementation for experimental and control clinics, respectively. Previous research also suggests that both groups will have the same standard deviation (SD = 4). Assuming an SD = 4, and a mean difference of 8 at post-implementation (2% vs 10%), power to detect a group by time interaction  $> .998$  with  $\alpha = .05$  and  $N = 28$  (18 experimental and 10 control clinics). If we are able to recruit adequately with only 10 experimental clinics (with  $N = 20$ , comprising 10 experimental and 10 control clinics), the smallest  $N$  that we can envision, then power = .887 with a smaller prognosticated post-implementation group difference (8 vs. 2%). Thus, power appears ample for conservative tests of our primary outcome. We will use other analytic strategies to analyze these data (e.g., General Estimating Equations) that model patients as the units of analysis, with patients being nested within clinics. Only aggregated (non-identifiable) data will be used for these analyses. Such approaches should have greater power than the approach described above, which we present for purposes of clarity and simplicity. In addition, in secondary analyses we will compare subcategories of treatment engagement rates: e.g., comparing WTQL engagement rates in the control clinics with engagement rates for *cessation* treatment in the experimental clinics (i.e., removing chronic care engagement data for smokers who wanted to reduce their smoking). We will also examine treatment completion rates and 6-month abstinence rates, especially for those referred to the chronic care treatment, to determine the “yield” of treatment referral. Such data would also allow us to compute cost-effectiveness and cost-benefit analyses.

The analytic approach that we have described above will also be used for the other major outcomes (i.e., smoker documentation and treatment referral). There is adequate power for both of these outcomes.

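### Clinic trial: the quoted group-by-time power cannot be verified without a pre-post correlation or a definition of SD = 4, and the ANCOVA leaves out baseline engagement

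*Combined protocol and SAP*

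**What the plan says.** The material is in the Clinic Randomized Control Trial part of the power section. Treatment engagement is the primary outcome, the clinic is the unit, and both a repeated measures ANOVA and an ANCOVA are named for it. Neither is designated primary. The contrast is on "treatment engagement means averaged over the periods of clinic participation (which may differ somewhat across clinics) pre and post implementation", with a 6-month baseline.

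The planning values are these: "we anticipate treatment engagement will be 1% for both groups at baseline", then "10 and 2% post-implementation for experimental and control clinics, respectively", with a common SD of 4. The power sentence reads "Assuming an SD = 4, and a mean difference of 8 at post-implementation (2% vs 10%), power to detect a group by time interaction" and gives a value above .998 for 18 experimental and 10 control clinics. For the smallest design, 10 and 10 clinics with 8% versus 2%, power is put at .887. The section concludes that power is ample.

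The ANCOVA will use "clinic location (rural vs. urban), size, SES, and baseline rates of smoker documentation and referral as covariates". Baseline engagement is not in that list. It is also not among the baseline covariates mentioned under Data Collection for the Clinic Randomized Control Trial, which names Quit Line referral and smoker documentation.

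**The concern.** With two groups and two periods, the group-by-time test is a t-test on each clinic's change. Its error depends on the baseline SD, the post SD and their correlation. The plan gives one SD, does not say which of these it is, and gives no correlation. The power statements for the mixed-model analyses in the three clinical studies do give a within-subject correlation (0.6).

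The gap matters most at the lower end of the 10 to 18 experimental clinics that the Study Design section allows, because the .887 is what supports going that low.

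Separately, the covariate list leaves out the pre-implementation value of the outcome itself. With 20 to 28 clinics that is an obvious variable to adjust for, and the plan already collects it.

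**Working it through.** **Inputs from the plan.** Clinics 18 vs 10 with difference 10 − 2 = 8, and 10 vs 10 with difference 8 − 2 = 6; SD 4; α = .05. Baseline is 1% in both groups, so the difference in change equals the post difference.

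**Assumptions needed.** Two-sided test; baseline SD b and pre-post correlation r ≥ 0, neither of which the plan gives.

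**Step 1: reproduce the plan's figures.** Noncentral t with ncp = difference / (SD × √(1/n₁ + 1/n₂)).
- 18 vs 10: 8 / (4 × 0.3944) = 5.071, df 26, power .9982.
- 10 vs 10: 6 / (4 × 0.4472) = 3.354, df 18, power .8870.

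Both match a post-only comparison with SD 4.

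**Step 2: when does the interaction give the same numbers?** With post SD 4, SD(change)² = 16 + b² − 8rb. This equals 16 when r = b/8, that is r = .125 for b = 1, .25 for b = 2, .375 for b = 3 and .5 for b = 4. The figures also follow directly if 4 is already the SD of change. Above r = b/8 the power is higher than stated; below it, lower.

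**Step 3: interaction power with post SD 4.**

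| Baseline SD | r | SD of change | 18 vs 10, diff 8 | 10 vs 10, diff 6 |
|---|---|---|---|---|
| 1 | 0 | 4.12 | .997 | .868 |
| 1 | .25 | 3.87 | .999 | .906 |
| 2 | 0 | 4.47 | .992 | .810 |
| 2 | .25 | 4.00 | .998 | .887 |
| 3 | 0 | 5.00 | .974 | .718 |
| 3 | .25 | 4.36 | .994 | .829 |
| 4 | 0 | 5.66 | .932 | .612 |
| 4 | .5 | 4.00 | .998 | .887 |

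**Step 4: how large can the baseline SD be?** Ten non-negative rates averaging 1% sum to 10. They are most spread when one clinic is at 10% and nine are at 0, which gives √((9² + 9 × 1²)/9) = √10 = 3.16. A ten-clinic arm with that mean cannot show a baseline SD of 4.

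**Step 5: ANCOVA of post engagement on condition and baseline engagement.** Take 4 as the post SD and baseline engagement as the only covariate. The residual SD is 4√(1 − r²), with one degree of freedom fewer. The upper figure in each pair ignores chance imbalance in the covariate; the lower multiplies the variance by (N − 3)/(N − 4) to allow for it.
- N = 20, r = 0: ncp 3.354, df 17, power .885; with the factor 17/16, ncp 3.254, power .866.
- N = 20, r = .5: ncp 3.354/.866 = 3.873, power .954; with the factor, ncp 3.757, power .943.
- N = 28, r = 0: ncp 5.071, df 25, power .998; with the factor 25/24, .997.

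Against Step 3, the ANCOVA at N = 20 is far better when the baseline SD is large (.866 to .885 against .718 at SD 3, r = 0). At a small baseline SD it is level with the change test or at most about .02 below it (.886 to .904 against .906 at SD 1, r = .25).

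**The case against.** The plan's figures reproduce exactly, and the interaction test gives the same figures under ordinary conditions. Baseline engagement is not ignored either: it is the pre level of the repeated measures ANOVA, and baseline referral, a step towards engagement, is an ANCOVA covariate. With engagement near 1% at baseline the baseline SD is probably small, and at an SD of 1 or 2 the 20-clinic power is at least .80 even at r = 0. With the main planned difference of 8, 20 clinics give .848 even at baseline SD 4 and r = 0 (ncp 8 / (5.657 × 0.4472) = 3.162, df 18). All of this stands. It limits the size of the point but does not supply the missing input or explain the missing covariate.

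A reader might infer four stronger things that the documents do not support.
- **That the figures are those of a post-only comparison and so wrong for the interaction.** The documents do not show which calculation was run, and both routes can give the same numbers.
- **That r must be at least .5.** This is so only if the baseline SD is also 4.
- **That 20-clinic power may be as low as .61.** That needs a baseline SD of 4, above the 3.16 limit in Step 4.
- **That the five listed covariates should leave the main model, so that "We will conservatively use ANOVA to estimate power" is mistaken.** Five wholly uninformative covariates would bring the 20-clinic power to about .74 (variance × 17/12, df 13), but nothing suggests that they are uninformative. The plan itself says their effect on error is unclear. Size, rural-urban setting and baseline Quit Line referral are also among the factors used to allocate clinics, so adjusting for them is defensible.

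**Conclusion.** The point holds as one of an unstated input and an omitted covariate, not of a proven error. The quoted power for the interaction cannot be verified from the plan. It is right if 4 is the SD of change and, with a post SD of 4, it is met or exceeded when r is at least b/8.

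The 28-clinic conclusion is robust: at least .93 for any r of 0 or more with baseline SD up to 4. Only the 20-clinic case with the 6-point difference is sensitive, at about .87, .81 or .72 for r = 0 and an assumed baseline SD of 1, 2 or 3. These baseline SDs are assumptions, and the smaller ones fit a 1% mean better.

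Leaving baseline engagement out of the ANCOVA forgoes protection that the planned data would give: about .87 to .885 at r = 0 and .94 to .95 at r = .5 with 20 clinics, provided 4 is the post-implementation SD.

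**What to change.** 1. Add the clinic's 6-month baseline engagement rate as a covariate in an ANCOVA of post-implementation engagement on condition, and name this as the primary test in place of the change-score interaction. This also settles which of the two named analyses is primary.
2. State whether SD = 4 is the SD at baseline, after implementation or of change, and tie each quoted power to that definition. If an interaction power is kept, give the assumed pre-post correlation and baseline SD with it.

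The power in Step 5 is for baseline engagement as the only covariate. Whether the five listed covariates also stay in the primary model is a trade-off for the sponsor; if they do, the 20-clinic power should be quoted for that model.

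The cost is one degree of freedom and a change of wording. No new data or clinics are needed.

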rural-urban setting, baseline rate of WTQL referral, and smoker prevalence. These criteria can be altered depending upon their pre-assignment availability. Thus, the approach involves: 1) Conducting a PC analysis in the pool of *potentially* available clinics (combined across the 2 healthcare systems) to identify a small number of uncorrelated PC's. 2) Integrating the PC's in a way that reflects the hypothesized direction of their impact on outcomes (inflating vs. reducing treatment engagement). 3) Locating all clinics available for randomization on a single dimension that reflects the hypothesized net impact of the PC's. 4) Forming two groupings of high and low clinics that are set using a cut-score imposed on the dimension composite. 5) The clinics are randomly assigned within and across sets in a manner that ensures that approximately an equal number of high and low ranking clinics are assigned within each condition. Thus, if a set of 6 clinics is being used for captive assignment, and this entails assigning 2 of the 6 to the control condition, one of the high scoring clinics and one of the low-scoring clinics will be randomly assigned to the control condition. Conversely, 2 of the high scoring and 2 of the low-scoring clinics must be assigned to the experimental condition (to complete an assignment set), exhausting this particular set. Thus, randomization to condition is nested within the high and low PC-score groupings. We will assign clinics to the two conditions on a 50/50 basis during early recruitment when the ultimate N (and mix of experimental and control clinics is unknown). Note that if the set of clinics is quite small (due to limited availability at a given point in time), it might be the case that only one clinic can be assigned to a particular condition in that set (e.g., to the control condition). In that case, in the next set the clinic assigned to the control condition must come from the other end of the PC risk dimension. In this way, the approach is flexible but nevertheless increases the likelihood that clinics are assigned to the two conditions at a similar rate over time, and that the two conditions are similarly balanced on factors thought to affect the dependent variables.

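### Clinic trial: the plan says patient-level GEE should have more power than the clinic-level analysis, but 20 to 28 randomised clinics give essentially no valid gain, and the usual uncorrected GEE would reject too often

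*Combined protocol and SAP*

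**What the plan says.** The power section for the Clinic Randomized Control Trial names treatment engagement as the primary outcome, to be analysed by repeated-measures ANOVA and ANCOVA. On the unit of analysis it says: "The analyses will, conservatively, use the clinic as the unit of analysis". Power is given for two sizes, "18 experimental and 10 control clinics" (above .998 for 10% vs 2%) and a smallest case "comprising 10 experimental and 10 control clinics" (.887 for 8% vs 2%), both with a standard deviation of 4.

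It then adds other strategies, with GEE as the example, "that model patients as the units of analysis, with patients being nested within clinics". Two sentences qualify these: "Only aggregated (non-identifiable) data will be used for these analyses" and "Such approaches should have greater power than the approach described above, which we present for purposes of clarity and simplicity".

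The assignment procedure under Study Design confirms that clinics are what is randomised: "Thus, randomization to condition is nested within the high and low PC-score groupings". The short paragraph after the power text carries the analytic approach over to smoker documentation and treatment referral.

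For the GEE, the plan gives no intraclass correlation, patients per clinic, working correlation, link, variance estimator, reference distribution, degrees of freedom or small-sample correction.

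**The concern.** In a trial that randomises clinics, precision is limited by the number of clinics and by how much their rates differ. Thousands of patients per clinic shrink only the sampling noise within a clinic, which is already small. Patient-level covariates could in principle add precision, but aggregated data do not supply them.

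A patient-level GEE can still appear more powerful. The ordinary sandwich variance is biased downwards when clusters are few, and a normal reference ignores the small degrees of freedom. Both push rejections above the nominal 5%, with or without a true effect.

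The plan calls the clinic-level analysis conservative and the GEE more powerful. If the clinic-level test were non-significant and the GEE significant, that wording would invite a reader to trust the GEE. The same could arise for documentation and referral if the GEE is carried over to them.

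**Working it through.** **Inputs from the plan.** Clinics: 18+10 or 10+10. SD of clinic engagement rates: 4 percentage points in both groups. Differences: 8 points (10% vs 2%) and 6 points (8% vs 2%). Alpha .05; sidedness is not stated, and two-sided reproduces the figures.

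**Assumed, not stated.** Smokers per clinic: Appendix 1 mentions about 100,000 patients. Read as a total over 18 clinics, that is 100,000/18 = 5,556 each. With an assumed 10-20% smoking, about 550-1,100 smokers per clinic. The coefficient of variation (CV) of clinic size is varied up to 1.0.

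**Step 1: reproduce the stated power.** Two-sample t test on clinic values, df = N - 2, noncentrality = difference / [SD x sqrt(1/n1 + 1/n2)]. For the group-by-time interaction this means a change score with SD 4, for example SD 4 at each time with pre-post correlation 0.5, since 2 x 16 x (1 - 0.5) = 16.
- 18+10, difference 8: 8 / (4 x .3944) = 5.07, df 26, power .9982 (plan: above .998).
- 10+10, difference 6: 6 / (4 x .4472) = 3.354, df 18, power .8870 (plan: .887).

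Both reproduce.

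**Step 2: what GEE does in the simplest case.** Take 10+10 equal-sized clinics, identity link, no covariates. The GEE estimate is then the difference in mean clinic rates, exactly as in the t test. Only the variance differs. With s² the sample variance of clinic rates in an arm of n clinics:
- Uncorrected sandwich: (n-1)s²/n². Rejecting at 1.96 means |t| > 1.96 x sqrt(9/10) = 1.859 on 18 df, a type I error of .079.
- Kauermann-Carroll (KC): s²/n. With a t reference on 18 df this is the clinic t test.
- Mancl-DeRouen (MD): s²/(n-1). Rejection needs |t| > 2.101 x sqrt(10/9) = 2.215, a type I error of .040.

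**Step 3: simulation with normal clinic means and equal sizes.** 20,000 replicates per setting (400,000 for the main null result); corrected versions use a t reference on residual df.

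| Quantity | Clinic t | GEE + KC | GEE + MD | GEE uncorrected |
|---|---|---|---|---|
| Type I error, 10+10 | .049 | .049 | .039 | .079 |
| Type I error, 18+10 | .048 | .052 | .045 | .075 |
| Power, 10+10, difference 6 | .884 | .884 | .861 | .926 |
| Power, 18+10, difference 6 | .958 | .956 | .944 | .971 |
| Power, 18+10, difference 8 | .998 | .998 | .998 | .999 |

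The uncorrected .926 comes from testing at about 8% instead of 5%. If the GEE also carried the five clinic-level covariates listed for the ANCOVA, its uncorrected type I error would be .155 (10+10) or .117 (18+10).

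**Step 4: binary data with unequal clinics.** Beta-binomial clinics, observed-rate SD 4 points, identity link, exchangeable working correlation, 550-1,100 smokers per clinic, size CV 0.6-1.0.
- Uncorrected type I error: .076-.081.
- Power, 8% vs 2%, 10+10: clinic t .824-.843, KC .830-.844, MD .812-.827.
- Power, 8% vs 2%, 18+10: clinic t .893-.908, KC .877-.883, MD .864-.872.

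With a logit link and exchangeable correlation, uncorrected type I error is .082-.088 at a 6% rate and .14-.17 at a 2% rate. An independence working correlation with very unequal clinics takes it to about .13 at a 6% rate.

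**Step 5: why the gain is so small.** At a 6% rate the binomial variance of a clinic's rate, in squared points, is 6 x 94 / m. For m = 550 this is 1.03, or 6% of the total variance of 16; for m = 1,100 it is 0.51, or 3%. Patient-level weighting can improve only on that share. At m = 50 it is 11.3, or 70%. That is where the largest valid gain appeared: KC .822 against clinic t .791, at 10+10 with size CV 1.0.

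**The case against.** Four points can be made for the plan.

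- **The clinic-level analysis already leads.** The primary outcome is assigned to it, both power figures rest on it, and GEE follows only as an example. A reader might infer that the GEE is meant to override it, or that the trial's power is in doubt. Neither is supported: the text places the clinic-level test first, and its power is correct and ample. This stands and limits the point to a supporting analysis.
- **No variance estimator is named.** A reader might infer that the plan chose an invalid test. It did not; it is silent. The excess error describes the usual default, which the plan leaves open. This also stands.
- **Corrected models can beat the ANOVA.** With one baseline covariate (SD 4 at each time, pre-post correlation 0.5, equal sizes, 10+10, difference 6), a corrected clinic-clustered model has simulated power of .94 (KC) or .91 (MD), against .88 for the change-score ANOVA. But that gain comes from baseline adjustment, which the planned clinic-level ANCOVA shares. It does not come from modelling patients, which is the plan's stated contrast.
- **Corrected GEE need not lose power.** A reader might infer a large loss from simulations of a 4-point difference with a logit link and independence working correlation (.45-.47 against .56). The plan specifies none of those three. With normal clinic means and equal sizes at the same difference, KC matches the t test (.566 for both) and MD gives .527. A general claim of lower power is therefore not supported, and neither is a claim that no gain is ever possible.

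**Conclusion.** The greater-power sentence is unsupported. Under the plan's own inputs, patient-level modelling gives essentially no valid gain over the clinic-level test: none with KC in the balanced equal-size case, a small loss with MD, and at most about 3 points in small, very unequal clinics. Left at the usual default, the supporting GEE would run at about 7.5-9% type I error in the main settings, and higher with unequal clinic sizes under an independence working correlation, with several clinic-level covariates, or at a low event rate with a logit link.

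This rests on an SD of 4 points between clinics, on aggregated data without patient covariates, and on the assumed range of smokers per clinic and size variation. A higher smoking rate, or reading the Appendix 1 figure as per clinic, would make clinics larger and the gain smaller still.

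The primary analysis stands. The point merits a change because the plan claims a property that the design lacks and leaves open the analysis default that would appear to confirm it.

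**What to change.** 1. Delete the sentence claiming greater power.
2. Specify the GEE: clinic as the cluster; the link and working correlation named; a small-sample-corrected sandwich (Kauermann-Carroll, or Mancl-DeRouen if clinic sizes prove very unequal); a t reference on clinic-based degrees of freedom, which is clinics minus 2 without covariates and fewer with them; and few clinic-level covariates.
3. Label the GEE as supportive of the clinic-level primary analysis, and say the same for documentation and referral if it is used there.

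The cost is a few lines of text and a software option. The GEE intervals become slightly wider, and Mancl-DeRouen is somewhat conservative with this few clinics (type I error about .04 at 10+10). Sample size, primary analysis and stated power do not change.
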